
STUDY POPULATION
 
Main selection criteria for the randomized treatment period
	
Inclusion criteria:
 
• Patients with type 2 diabetes mellitus diagnosed at least one year prior to screening visit (V1);• Patients who have been treated with one of the following GLP-1 receptor agonists for at least 4 months prior to screening visit (V1), and with stable dose for at least 3 months prior to screening visit (V1):
- Liraglutide (Victoza®) 1.8 mg once daily (QD) or 1.2 mg QD, if 1.8 mg QD is not well tolerated according to Investigator's judgment;- or Exenatide twice daily (BID) (Byetta®) 10 µg BID or of 5 µg BID, if 10 µg BID is not well tolerated according to Investigator's judgment;in combination with metformin (daily dose ≥1500 mg/day or Maximum Tolerated Dose (MTD)), with or without pioglitazone, with or without SGLT2 inhibitor, all at stable dose for at least 3 months prior to screening; 
or
 
• Patients who have been treated with stable dose of one of the following GLP-1 receptor agonists for at least 6 months prior to screening visit (V1):
- Exenatide extended-release (Bydureon®) 2 mg once weekly (QW), if well tolerated according to Investigator's judgment;- Albiglutide (Tanzeum®) 50 mg QW or 30 mg QW, if 50 mg QW is not well tolerated according to Investigator's judgment;- Dulaglutide (Trulicity®) 1.5 mg QW or 0.75 mg QW, if 1.5 mg QW is not well tolerated according to Investigator's judgment.in combination with metformin (daily dose ≥1500 mg/day or MTD), with or without pioglitazone, with or without SGLT2 inhibitor, all at stable dose for at least 3 months prior to screening;• Signed written informed consent. 
Exclusion criteria:
 
• At screening visit (V1), age <legal age of adulthood;• Screening HbA1c <7% (53 mmol/mol) and >9% (75 mmol/mol);• Pregnancy or lactation, women of childbearing potential with no effective contraceptive method;• Any use of anti-diabetic drugs within 3 months prior to the screening visit (V1), other than those described in the inclusion criteria;• Previous treatment with insulin in the year prior to screening visit (V1) (note: short term treatment with insulin (≤10 days) due to intercurrent illness including gestational diabetes is allowed at the discretion of the study physician);• Laboratory findings at the time of screening, including:
- Fasting Plasma Glucose (FPG) >250 mg/dL (13.9 mmol/L);- Amylase and/or lipase >3 times the upper limit of the normal laboratory range (ULN);- Alanine aminotransferase (ALT) or Aspartate aminotransferase (AST) >3ULN;- Calcitonin ≥20 pg/mL (5.9 pmol/L);- Positive serum pregnancy test.

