
ENDPOINT(S)
	
Primary endpoint:
 
 • Change in HbA1c from baseline to Week 26. 
Secondary endpoint(s):
 
Efficacy
 
 • Percentage of patients reaching HbA1c <7 % (53 mmol/mol) or ≤6.5% (48 mmol/mol) at Week 26; • Change in FPG from baseline to Week 26; • Change in 7-point SMPG profiles from baseline to Week 26 (each time point and average daily value); • Change in 2-hour PPG and in blood glucose excursion during standardized meal test from baseline to Week 26; • Percentage of patients requiring rescue therapy during the 26 week treatment period; • Change in body weight from baseline to Week 26. 
Other endpoints:
 
 • Insulin glargine and lixisenatide doses at Week 26 in the combination group; • C-peptide evaluation during standardized meal test from baseline to Week 26; • Percentage of patients reaching HbA1c <7% (53 mmol/mol) with no body weight gain from baseline to Week 26; • Percentage of patients reaching the fasting SMPG target (≤100 mg/dl) at Week 26 in the FRC group; • Percentage of patients with no weight gain at Week 26; • Pharmacokinetics parameters (FRC group): Total plasma concentrations of lixisenatide will be assessed in the time frame from 1 to 4 hours post-injection at Day 1 of the treatment phase and prior to injection as well as in the time frame from 1 to 4 hours post injection at Week 4, Week 12, Week 26. 
Safety endpoints:
 
 • Symptomatic hypoglycemia (documented, probable, severe symptomatic hypoglycemia); • Adverse events (AE), serious adverse events (SAE), adverse event of special interest (AESI), AEs requiring specific monitoring and reporting on specific electronic case report forms (e-CRFs) (suspected allergic reactions, patients with increased pancreatic enzymes >2 ULN/pancreatic events, patients with increased calcitonin ≥20 pg/mL, Device-related events (DRE)); • Safety laboratory values; • Vital signs; • Electrocardiogram (ECG); • Immunogenicity (antibody variables, FRC group): anti-insulin and anti-

[figure not shown]
	
lixisenatide antibodies.
 
Endpoints of the extension period
 
All primary and secondary efficacy, safety, PK and other endpoints will be also assessed at the end of the extension period (Week 52).

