In the post-marketing experience with GLP-1 receptor agonists, spontaneously reported cases of pancreatitis raised concerns that drugs in this class could cause pancreatitis. Therefore, patients enrolled in this study should be followed for any evidence of suspected pancreatitis, eg, with symptoms and/or signs of acute abdominal distress or abnormal levels of pancreatic enzymes. Serum amylase and lipase concentrations are to be monitored routinely at screening, baseline and periodically during the study treatment period. As this monitoring may be difficult to interpret in patients who already have high values of amylase or lipase, patients with values above 3 times the upper limit of normal range at screening will not be included in the study. Guidance for Investigators on the follow-up of suspected pancreatitis is specified in the protocol. In addition, a Pancreatic Safety Assessment Committee (PSAC) has been established. The PSAC is a committee of experts in the field of pancreatitis and pancreatic neoplasm, independent from the Sponsor and the Investigators, implemented to assess pancreatic events that may occur during the study.

Information from Victoza® (liraglutide) (6, 7), Bydureon® (exenatide-extended release) (10, 11), Tanzeum® (albiglutide) (, 12), and Trulicity® (dulaglutide) (13, 14) pre-clinical carcinogenicity studies has raised the issue of a potential increased risk of thyroid C-cell hyperplasia and neoplasm. Following a request from the health authorities concerning any clinical study longer than 3 months with a GLP-1 receptor agonist, serum calcitonin will be monitored in this study as a marker of thyroid C-cell hyperplasia and neoplasm, with specific monitoring implemented for patients with value ≥ 20 pg/mL (5.9 pmol/L). As this monitoring may be difficult to interpret in patients who already have high values, those with calcitonin values equal to or above 20 pg/mL (5.9 pmol/L) at screening will not be included in the study.

Like any other peptide product, there is a potential for antibody generation when treated with the FRC. Therefore, assessments of the immunogenicity of insulin glargine and lixisenatide will be performed. Antibodies against insulin glargine are well characterized. Therefore, assessment of anti-insulin antibodies is limited to antibody titers and cross-reactivity to human insulin. For lixisenatide, the time course of formation of antibodies and antibody concentrations will be

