- Patients with conditions/concomitant diseases precluding their safe participation in this study (eg, malignant tumor within 5 years prior to screening visit (V1), major systemic diseases, presence of clinically significant diabetic retinopathy or presence of macular edema likely to require treatment within the study period);
- Impossibility to meet specific protocol requirements (eg, scheduled visits, patients unable to fully understand patient's study documents and to complete them);
- Patient is uncooperative or has a condition that could lead to non-compliance with the study procedures (eg, patient unable or unwilling to do self-injections or blood glucose monitoring using the sponsor-provided blood glucose meter at home);
- Patient is the Investigator or any Sub-Investigator, research assistant, pharmacist, study coordinator, other staff or relative thereof directly involved in the conduct of the protocol;
- Patients with short life expectancy;
- Requirement for concomitant treatment that could bias primary evaluation.

E 17. Laboratory findings at the screening visit:

- Fasting Plasma Glucose (FPG) >250 mg/dL (13.9 mmol/L);
- Amylase and/or lipase: >3 times the upper limit of the normal (ULN) laboratory range,
- Alanine aminotransferase (ALT) or aspartate aminotransferase (AST): >3 ULN;
- Total bilirubin >1.5 ULN (except in case of Gilbert's syndrome);
- Calcitonin \geq 20 pg/mL (5.9 pmol/L);
- Hemoglobin <10.5 g/dL or neutrophils <1,500/mm³ or platelets <100,000/mm³;
- Positive test for Hepatitis B surface antigen (HBsAg) and/or Hepatitis C antibody (HCAb);
- Positive serum pregnancy test in females of childbearing potential.

E 18. Patient who has renal function impairment with estimated glomerular filtration rate (GFR) <30 mL/min/1.73m² (using the MDRD [[Appendix A](#)]) or end-stage renal disease;

E 19. Any technical/administrative reason that makes it impossible to randomize the patient in the study;

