10.6.4 Monitoring of patients with increased lipase and/or amylase >2x ULN

Potential safety signals for acute pancreatitis have been identified in the post-marketing experience of other GLP-1 receptor agonists. Therefore, patients enrolled in this study should be followed for any suspected pancreatitis, eg, with symptoms and/or signs of acute abdominal distress or abnormal levels of pancreatic enzymes. Serum amylase and lipase concentrations are monitored routinely at screening, baseline and periodically during the study treatment period.

In the presence of clinical signs and/or symptoms evocative of pancreatitis, eg, persistent abdominal pain, which can radiate to the back, often with characteristic positional features, with possible occurrence of nausea, vomiting, fever and leukocytosis, further measurement of amylase and lipase should be performed. The clinical signs and/or symptoms should be documented in the source data.

(1) Elevation of Amylase and/or Lipase >2x ULN without clinical signs and/or symptoms

In any case where amylase and/or lipase are >2x ULN, a retest (centrally assessed as far as possible) must be performed as follows:

- If value(s) is/are >2-3x ULN: retest within 7 days;
- If value(s) is/are >3x ULN: retest within 48 hours;
- If the value(s) remain(s) >2x ULN upon retesting: amylase and/or lipase levels should be retested weekly until values are <2x ULN.

In case a retest is >2x ULN a gastroenterological evaluation and imaging (ultrasound and/or CT or MRI with contrast, as appropriate) must be performed. Please document in the source data the absence of clinical signs and/or symptoms (if clinical signs and/or symptoms develop, please see part (2) below).

Best clinical judgment is to be used when interpreting elevated serum amylase and lipase levels in asymptomatic patients. Temporary discontinuation of the IMP may be considered in these cases if deemed necessary by the Investigator.

(2) Elevation of Amylase and/or Lipase >2 x ULN with clinical signs and/or symptoms

In the presence of clinical signs and/or symptoms evocative of pancreatitis (as described above) associated with elevated amylase and/or lipase, treatment with the IMP should be promptly and at least temporarily discontinued pending further clinical evaluation and diagnosis confirmation.

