 - The number (%) of patients with events reported on the AE form for increased lipase and/or amylase >2 times ULN and its associated complementary forms will be summarized by PTs for each treatment group, sorted by decreasing incidence of PT.
 - The number (%) of patients with events positively adjudicated as pancreatitis by the PSAC will be summarized by type: 1) acute pancreatitis, 2) acute exacerbation of chronic pancreatitis, 3) chronic pancreatitis, 4) unknown pancreatitis.

- All events sent to PSAC for adjudication of pancreatitis (ie, events reported on the AE form for increased lipase and/or amylase > 2 times ULN) will be listed along with the adjudication outcome.
- Pancreatic neoplasm
 - All the events sent to PSAC for adjudication for pancreatic neoplasm will be listed along with the adjudication outcome including PSAC diagnosis, type of neoplasm (malignant, benign, not determined), cancer stage etc.

Increased calcitonin

The number (%) of patients with events reported on the AE form for increased calcitonin ≥ 20 pg/mL and its associated complementary forms will be summarized by PTs for each treatment group, sorted by decreasing incidence of PT in the FRC group. In addition, a listing of those patients will be provided.

ALT increase

The number (%) of patients with events reported on the AE form for ALT increase and its associated complementary forms will be summarized by PT for each treatment group, sorted by decreasing incidence of PT in the FRC group. In addition, a listing of those patients will be provided.

Device-related events

The number (%) of patients with events reported on device-related event questionnaire will be summarized for each treatment group along with 2 subcategories, events associated with a clinical event (either symptomatic hypoglycemic event or adverse event) and events not associated with a clinical event. The number of events and rates in patient year will also be summarized as appropriate. The number (%) of patients who have device-related events with lixisenatide dose $< 5 \mu\text{g}$, $> 20 \mu\text{g}$ within the corresponding time window (from event start date to event end date or to treatment end date if event end date is missing) of device-related event will be summarized for FRC group only. In addition, a listing of patients with those events will be provided.

Analysis of pre-treatment and post-treatment adverse events

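### The by-arm count of amylase/lipase above 2x ULN can include patients who entered above that level: entry is barred only above 3x ULN, and the table takes no account of baseline

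*Protocol*

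**What the plan says.** **Entry.** Criterion E 17 (Protocol 7.2.1) excludes on the screening value "Amylase and/or lipase: >3 times the upper limit of the normal (ULN) laboratory range"; the synopsis sets the same limit. Section 4 gives the reason, "As this monitoring may be difficult to interpret in patients who already have high values of amylase or lipase", and concludes that "patients with values above 3 times the upper limit of normal range at screening will not be included in the study".

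**Event.** The synopsis and Protocol 9.2.2 list, among the safety endpoints, "patients with increased pancreatic enzymes >2 ULN/pancreatic events". Section 10.6.4 sets the follow-up rule: "In any case where amylase and/or lipase are >2x ULN, a retest (centrally assessed as far as possible) must be performed as follows". If the retest is also above 2x ULN, the section calls for weekly retests, a gastroenterological evaluation and imaging even without symptoms, and for reporting on the dedicated AE form. SAP 2.1.4.2 defines the event as an entry on that form confirmed by a repeated test. None of these places asks for a rise over the patient's own baseline.

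**Table.** SAP 2.4.5.2 summarises, by preferred term and treatment group, "The number (%) of patients with events reported on the AE form for increased lipase and/or amylase >2 times ULN". Protocol 11.4.6.2 plans the same table.

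**Neighbouring limits.** For calcitonin, the exclusion and the monitored event both start at 20 pg/mL. For ALT, the exclusion and the adverse event of special interest are both above 3x ULN.

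**The concern.** The protocol's stated reason for an entry limit is that an already high value makes monitoring hard to interpret. A patient at 2.5x ULN fits that description, since the first routine on-treatment draw can meet the event threshold with no change at all. Yet that patient is eligible. For calcitonin and ALT the entry limit and the event limit coincide, so the gap is specific to the pancreatic enzymes.

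What is at stake is how one safety table can be read. If the percentage with confirmed values above 2x ULN mixes new elevations with elevations brought into the trial, the reader cannot tell how much is new under treatment. This is a signal the protocol singles out with its own monitoring rules, AE form and adjudication committee.

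**Working it through.** The plan states no count or rate on this point, so there is no figure to reproduce. The check has three parts.

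**1. The rules side by side**

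| Step | Limit | Depends on baseline? |
|---|---|---|
| Exclusion (synopsis, Section 4, E 17) | above 3x ULN at screening | – |
| Retest (10.6.4) | above 2x ULN | no |
| Imaging and weekly retests (10.6.4) | retest above 2x ULN | no |
| AE form (10.6.4; SAP 2.1.4.2) | confirmed above 2x ULN | no |
| By-arm table (Protocol 11.4.6.2; SAP 2.4.5.2) | form present | no split; treatment emergence not stated |

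The band above 2x and up to 3x ULN is thus open at entry and inside the event definition.

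**2. Who can be counted without a true rise**

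Treatment emergence turns on when an event developed, worsened or became serious (Protocol 11.4.6.2; SAP 2.1.4.2). AEs are collected from consent, and enzymes are drawn at V1 and V3. An elevation seen in those samples has its onset before dosing and, if stable, is not treatment-emergent. Two routes remain:

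- *Fluctuation.* A patient above 2x ULN at one pre-dose draw and below it at the next can cross again on treatment and be recorded as new.
- *Unclear onset.* V3 is also Day 1, and a value between 2x and 3x ULN is to be retested within 7 days, so confirmation can fall after the first dose. If the onset date is incomplete, SAP 2.4.5.2 and 2.5.3 classify the event as treatment-emergent unless the information shows otherwise.

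**3. Illustrations**

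The documents give neither the share of patients entering above 2x ULN nor the within-patient variation. All inputs below other than 250 per arm, the 2x limit and the visit schedule are assumptions.

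*Number of patients.* Expected per arm = 250 × p; chance of at least one = 1 − (1 − p)^250.

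| Share p | Expected per arm | Chance of at least one |
|---|---|---|
| 0.5% | 1.25 | 71% |
| 1% | 2.5 | 92% |
| 2% | 5 | 99% |
| 5% | 12.5 | >99.9% |

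*Chance of a confirmed value with no true change.* There are four scheduled on-treatment draws in the randomized period (V7, V11, V21, V28). Take a stable median level m (in multiples of ULN), lognormal variation with s = √ln(1 + CV²), and an independent retest. Then q = 1 − Φ((ln 2 − ln m)/s), and the chance of at least one confirmed value is 1 − (1 − q²)^4. For m = 2.5 and CV 20%, q = 0.870, q² = 0.757 and the result is 1 − 0.243^4 = 0.997. Over CV 10% to 30% the range is 79–92% at m = 2.1, 97–100% at m = 2.5 and above 99% at m = 2.9. This is the chance of a confirmed laboratory value, not of being classed as treatment-emergent.

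*Effect on the contrast.* Suppose new elevations in 4% (FRC) and 2% (control), plus an equal share b% in each arm counted because of the entry value. The ratio is (4 + b)/(2 + b) and the difference is (4 + b) − (2 + b).

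| b | Ratio | Difference (points) |
|---|---|---|
| 0 | 2.00 | 2 |
| 1 | 1.67 | 2 |
| 2 | 1.50 | 2 |
| 4 | 1.33 | 2 |

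**The case against.** The case for leaving the plan alone has four parts.

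- **Onset governs, not filing.** A reader might infer that every patient entering between 2x and 3x ULN will be counted, or that an elevation first reported on treatment counts as new. The documents do not support that. Classification follows onset or worsening, the investigator records the onset date, and pre-treatment AEs are described separately. Read literally, 10.6.4 would also prompt a retest at screening, which lasts at least a week, so many such patients would be on record before dosing. This stands. It narrows the problem to fluctuating values and unclear onset, provided the treatment-emergent definition is applied to this table, which the plan does not say.
- **Baseline is used elsewhere.** SAP 2.4.5.4 plans changes from baseline and summaries of potentially clinically significant abnormalities by baseline status. This stands in part. Those are different tables, the split by baseline status is optional as worded, and the enzyme limits sit in an appendix that is not in the text reviewed.
- **No bias between arms.** A reader might infer that a treatment difference is hidden. Safety analyses are descriptive, no ratio or test is planned, and randomization balances entry values on average. This stands: the absolute difference is not biased. Only the level of each percentage and the relative contrast are affected.
- **Two limits can coexist.** An entry limit and a lower follow-up trigger are not a contradiction in themselves, and 10.6.4 leaves interpretation in asymptomatic patients to clinical judgment. This stands too. What remains is that the reason given in Section 4 is not carried through to patients who enter above 2x ULN.

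**Conclusion.** The point holds in a limited form. Patients above 2x and up to 3x ULN are eligible, the event has no baseline condition, and the table is neither split by baseline nor stated to be treatment-emergent only. Some patients can therefore be counted without a true on-treatment rise, mainly those fluctuating around 2x ULN or with unclear onset.

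The effect is inflation of both percentages and dilution of their ratio if the shares are similar in each arm. The absolute difference is not biased. The size is unknown, because the figures above rest on assumed shares, event rates and within-patient variation. One descriptive safety table is affected; no primary or formally tested endpoint is. Adjudicated pancreatitis is reported separately by the independent committee's outcome and does not depend on this count. This is a worthwhile, nearly free clarification rather than a flaw that threatens the trial's conclusions.

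**What to change.** In SAP 2.4.5.2, and in parallel in Protocol 11.4.6.2:

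1. State that the AE-form table for lipase and/or amylase above 2x ULN is limited to treatment-emergent events.
2. Present it by last pre-IMP value, at or below 2x ULN versus above 2x ULN, keeping both rows and the total. Say whether the class is set by the enzyme that triggered the event or by either enzyme.

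The values are already collected at V1 and V3. The cost is one small extra row and a slightly smaller count in the lower row. The split will not remove patients who start just under 2x ULN and drift across it; the planned change-from-baseline summaries help there.

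Separately, the sponsor should reconcile the entry limit and its rationale (Section 4, E 17) with the retest and imaging trigger in 10.6.4 for patients who enter above 2x ULN. No view is given here on which threshold is right.

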5 STUDY OBJECTIVES

5.1 PRIMARY

The primary objective of this study is to demonstrate the superiority of the insulin glargine/lixisenatide fixed ratio combination (FRC) versus GLP-1 receptor agonist in HbA1c change from baseline to Week 26.

5.2 SECONDARY

The secondary objectives of the study are to assess the effects of the FRC versus GLP-1 receptor agonist over 26 weeks on:

- Percentage of patients reaching HbA1c targets;
- Fasting Plasma Glucose (FPG);
- 7-point Self- Monitored Plasma Glucose (SMPG) profile;
- Glycemic control in relation to a meal as evaluated by 2-hour Post-prandial Plasma Glucose (PPG) and glucose excursion during a standardized meal test;
- Body weight;
- To assess the safety and tolerability in each treatment group.

5.3 OTHER OBJECTIVES

- To assess insulin glargine and lixisenatide doses in the combination group;
- To assess the development of anti-insulin antibodies (FRC group);
- To assess the development of anti- lixisenatide antibodies (FRC group);
- To assess the total plasma concentration of lixisenatide before and following injection (FRC group).

